### **Atezolizumab**

There will be no dose modifications for atezolizumab in this study.

## Appendix 6: Safety Plan: Management of Identified and Potential Risks

### **Carboplatin and Etoposide**

Dose modifications for carboplatin and etoposide are permitted for toxicity according to the prescribing information and local standard of care.

### **A6-2.2 CRITERIA FOR TREATMENT CONTINUATION DURING MAINTENANCE PHASE**

If a participant experiences adverse events during the maintenance treatment phase, the criteria outlined in [Table A6-2](#) must be met in order to continue study treatment.

**Table A6-2 Criteria for Treatment Continuation in Arm A During the Maintenance Phase**

	Lurbinectedin	Atezolizumab
	Day 1	Day 1
ANC	$\geq 1.5 \times 10^9/L$ for participants of non-African descent or $\geq 1.3 \times 10^9/L$ for participants of African descent	No defined requirements
Platelets	$\geq 100 \times 10^9/L$	No defined requirements
Hemoglobin a	$\geq 9 \text{ g/dL}$	
Total bilirubin (or direct bilirubin)	$\leq 1.5 \times \text{ULN}$ For participants with known Gilbert disease: total bilirubin $\leq 3 \times \text{ULN}$	
AST/ALT	$\leq 2.5 \times \text{ULN}$ For participants with documented metastatic liver disease, AST and ALT levels $\leq 5 \times \text{ULN}$	
Serum creatinine	$\leq 1.5 \times \text{ULN}$ or creatinine clearance $\geq 30 \text{ mL/min}$	
TSH b	No defined requirements	Within normal range If TSH is above ULN, T4 must be within normal range
Muscular toxicity (myalgia, muscular weakness, CPK increase, rhabdomyolysis)		Grade 1 or better
Immune-related toxicities (colitis, pneumonitis, endocrinopathies c and others)	No defined requirements	Grade 1 or better
Other non-hematological drug-related adverse events (except increased GGT, amylase/lipase, nausea and vomiting, alopecia, asthenia, dermatologic events, and/or neuropathy d )		Grade 1 or better

## Appendix 6: Safety Plan: Management of Identified and Potential Risks

---

**Table A6-2 Criteria for Treatment Continuation in Arm A During the Maintenance Phase**

	Lurbinectedin	Atezolizumab
	Day 1	Day 1
Active infection (including sepsis) and/or bleeding (any grade)		Absence

CPK = creatine phosphokinase; GGT = gamma-glutamyl transferase; ULN = upper limit of normal.

- a Participants may receive packed red blood cells transfusion and/or erythropoietin treatment, if clinically indicated, to increase or maintain adequate hemoglobin levels.
- b See Section [A6-2.4.2](#) for more information on management guidelines of endocrine event.
- c For Grade 2 endocrinopathies, please see [Table A6-5](#) for more details.
- d Any grade is accepted for increased GGT. Amylase and/or lipase increases of up to  $2.0 \times$  ULN are allowed. Up to Grade 2 is allowed for alopecia, neuropathy, asthenia, dermatologic events, and nausea or vomiting.

If a participant does not meet the requirements for re-treatment on Day 1 of Cycle 2 or any subsequent cycles, reassessments will be performed at least every 48–72 hours.

Treatment with lurbinectedin can be withheld up to a maximum of 3 weeks.

Participants not meeting re-treatment criteria after withholding lurbinectedin for a maximum of a 3-week delay should discontinue lurbinectedin treatment. In case of objective clinical benefit, the participant could continue to receive lurbinectedin treatment upon the Sponsor's agreement.

Participants may continue with atezolizumab as a single agent in case lurbinectedin is discontinued.

In case atezolizumab is discontinued due to an immune-related severe adverse event, treatment with lurbinectedin may continue as a single agent. If immune toxicity re-occurs despite discontinuation of atezolizumab, the participant will also discontinue lurbinectedin. Up to 2 dose reductions of lurbinectedin are allowed.

### **Chemotherapy**

Dose modifications for carboplatin and etoposide are permitted for toxicity according to the prescribing information and local standard of care.

## Appendix 6: Safety Plan: Management of Identified and Potential Risks

---

### **A6–2.3 TREATMENT INTERRUPTION**

Dose interruptions of study treatment may occur at any time and independently from each other at the discretion of the investigator for management of adverse events.

#### **A6–2.3.1 Lurbinectedin**

Lurbinectedin treatment may be temporarily suspended in participants experiencing toxicity considered to be related to lurbinectedin.

The administration of a new cycle of lurbinectedin should be delayed if the re-treatment criteria for adequate organ function are not met on Day 1 of the next scheduled cycle. Parameters will be periodically reevaluated until appropriate recovery. A maximum delay of 21 days will be allowed for recovery from treatment-related adverse events. If recovery has not occurred after a 21-day delay, the participant should discontinue lurbinectedin, except in case of clear evidence of objective benefit per investigator's judgment. The Medical Monitor is available to advise as needed. Participants who remain on lurbinectedin treatment after a 21-day delay because of the reasons described above, will do so after appropriate dose reduction of lurbinectedin.

#### **A6–2.3.2 Atezolizumab**

Atezolizumab treatment may be temporarily suspended in participants experiencing toxicity considered to be related to atezolizumab. If corticosteroids are initiated for treatment of the toxicity, they must be tapered over  $\geq 1$  month to  $\leq 10$  mg/day oral prednisone or equivalent before atezolizumab can be resumed. Treatment with atezolizumab may be resumed if the event improves to Grade 1 or better within 12 weeks and if corticosteroids have been reduced to  $\leq 10$  mg/day oral prednisone or equivalent within 12 weeks. If atezolizumab is withheld for  $> 12$  weeks (or 4 cycles) of initiating steroids, the participant will be discontinued from atezolizumab.

Atezolizumab treatment may be suspended for reasons other than toxicity (e.g., surgical procedures) at the investigator's discretion. The acceptable length of treatment interruption must be based on the investigator's benefit–risk assessment and in alignment with the protocol requirements for the duration of treatment and documented by the investigator. The Medical Monitor is available to advise as needed.

For guidelines on treatment interruption to manage specific adverse events associated with atezolizumab and lurbinectedin, see Section [A6–2.4.1](#) for lurbinectedin and Section [A6–2.4.2](#) for atezolizumab.

## Appendix 6: Safety Plan: Management of Identified and Potential Risks

---

### **A6–2.4 MANAGEMENT GUIDELINES**

#### **A6–2.4.1 Guidelines for Management of Adverse Events Associated with Lurbinectedin**

##### **A6–2.4.1.1 Management of Hematological Abnormalities**

Regular monitoring of hematological tests, including differential WBC counts will be performed prior to each dose administration and in addition, on Day 10 of Cycle 1 and Cycle 2 (see the schedule of activities in Section 1.3, Table 2) in order to allow re-treatment of participants with lurbinectedin.

Participants with hematologic toxicities may require additional or more frequent laboratory tests according to institutional guidelines. The administration of a new cycle of lurbinectedin should be delayed until the participant's blood counts have reached adequate levels. [Table A6-3](#) provides treatment guidelines for severe cases of neutropenia and thrombocytopenia deemed related to lurbinectedin.

Dose adjustment, if applicable, should always be considered in participants who experience febrile neutropenia, neutropenic infection, sepsis or Grade 4 neutropenia or thrombocytopenia in prior cycles. Supportive care for thrombocytopenia or anemia, such as transfusions, may be managed according to institutional guidelines.

Extensive early antibiotic coverage and all available supportive measures as indicated should be applied during a febrile neutropenia episode or Grade 4 neutropenia with clinical or epidemiological signs of infection after lurbinectedin treatment.

Conversely, the presence of fever or signs of infection during the second week after lurbinectedin treatment start (usually from Days 8–18) must always motivate a thorough clinical examination and complete blood counts, including differential WBC counts.

No increase in opportunistic infections associated with lymphopenia or prolonged Grade 4 neutropenia (more than 2 weeks) has been described in trial participants with solid tumors, although no specific conclusions may be drawn due to the lack of randomized data. Nevertheless, no prophylactic antibiotic coverage is indicated at current available clinical guidelines/recommendations.

## Appendix 6: Safety Plan: Management of Identified and Potential Risks

---

**Table A6-3 Lurbinectedin Management Guidelines for Hematological Abnormalities**

Event	Management
Grade 1, 2 or 3 neutropenia or Grade 1, 2 or 3 thrombocytopenia without bleeding	

Manage according to institutional practice.

Continue lurbinectedin when ANC is <math>\geq 1.5 \times 10^9/L</math> for participants of non-African descent or <math>\geq 1.3 \times 10^9/L</math> for participants of African descent and when platelets are <math>\geq 100 \times 10^9/L</math>.

Neutropenia Grade 4 or any grade of febrile neutropenia	

Interrupt lurbinectedin.

Restart lurbinectedin, at reduced dose, when ANC <math>\geq 1.5 \times 10^9/L</math> for non-African descent or ANC <math>\geq 1.3 \times 10^9/L</math> for African descent and resolution of any infections.

Thrombocytopenia Grade 3 with bleeding or Grade 4	

Interrupt lurbinectedin until platelet count <math>\geq 100 \times 10^9/L</math> (100,000/<math>\mu</math>L) and resolution of any bleeding.

Restart lurbinectedin at reduced dose.

### **A6-2.4.1.2 Management of Liver Abnormalities**

If Grade 3/4 increases in liver function tests (LFTs) are found, dose reduction and/or delays until resolution to at least Grade 1 are indicated. Re-evaluation before re-treatment is mandatory.

It is recommended that participants with elevation of ALT, AST, and/or bilirubin have more frequent laboratory monitoring of these parameters. If possible, hepatotoxic concomitant medications should be discontinued in participants who develop increased values of ALT, AST, or bilirubin and other causes (e.g., cancer-related, or infection) should be evaluated.

Management guidelines for hepatotoxicity related to lurbinectedin treatment are provided in [Table A6-4](#).

## Appendix 6: Safety Plan: Management of Identified and Potential Risks

**Table A6-4 Lurbinectedin Management Guidelines for Liver Abnormalities**

Severity of Transaminase (ALT or AST) Elevations by NCI CTCAE	Management
Grade 1 or 2	

• Dose reduction is usually not required.

• Consider discontinuing concomitant hepatotoxic medications and adding supportive care as indicated.

Grade $\geq 3$	

• Interrupt lurbinectedin and consider more frequent monitoring of ALT and/or AST.

• Restart lurbinectedin at a reduced dose when AST and ALT <math>\leq 2.5 \times</math> ULN (or for participants with documented metastatic liver disease, AST and ALT levels <math>\leq 5 \times</math> ULN).

• Discontinue if laboratory abnormalities cannot be reversed despite interruption of lurbinectedin.

NCI CTCAE = National Cancer Institute Common Terminology Criteria for Adverse Events; ULN = upper limit of normal.

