## A6-2 MANAGEMENT OF PARTICIPANTS WHO EXPERIENCE ADVERSE EVENTS

### A6-2.1 DOSE MODIFICATIONS

#### Lurbinectedin

Dose modifications for lurbinectedin are as follows:

- Up to 2 individual lurbinectedin dose reductions are allowed ([Table A6-1](#)). Once the dose has been reduced for an individual participant, it must not be re-escalated again under any circumstances. Participants who continue to experience treatment-related toxicity and/or frequent dose delays after permitted dose reductions must discontinue treatment with lurbinectedin. They can continue receiving the study medication if objective clinical benefit is adequately documented by the investigator, and upon agreement with the Sponsor. If the participant receives a lurbinectedin dose of 2 mg/m^2 and experiences a toxicity that would warrant a lurbinectedin dose reduction, treatment with lurbinectedin must be permanently discontinued.

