## Appendix 6: Safety Plan: Management of Identified and Potential Risks

---

- Participants may continue lorbinecetin at a reduced dose after they have adequately recovered from any of the following:
  - Grade  $\geq 3$  treatment-related non-hematological toxicity
  - Grade 4 thrombocytopenia or Grade 3 thrombocytopenia concomitantly with Grade  $\geq 3$  bleeding
  - Grade 4 neutropenia, any Grade febrile neutropenia or neutropenia associated with infection/sepsis
  - Frequent or prolonged ( $> 1$  week) dose delay due to treatment-related adverse events

Refer to [Table A6-2](#) for a list of criteria for treatment continuation.

Exceptions: patients experiencing treatment-related Grade  $\geq 3$  nausea and/or vomiting not optimally treated, Grade 3 asthenia lasting  $\leq 3$  days, Grade 3 diarrhea lasting  $\leq 2$  days or not optimally treated, Grade 3 transient ALT/AST elevations which are rapidly reversible and not leading to subsequent delays, and non-clinically relevant biochemical abnormalities, may continue treatment at the same prior dose without any dose reduction being applied, provided optimal concomitant treatment is given for the applicable toxicity.

Participants who experience Grade 3 or Grade 4 hypersensitivity reactions or Grade 3 or Grade 4 rhabdomyolysis will be discontinued from lorbinecetin.

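### The protocol's three lurbinectedin dose instructions after a Grade 3 ALT/AST elevation do not agree, and any dose reduction is permanent

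*Protocol*

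**What the plan says.** Three places in Protocol Appendix 6 deal with lurbinectedin after a Grade 3 ALT or AST elevation.

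- **Section A6-2.1 (Dose Modifications).** The general rule is a reduced dose after recovery from Grade 3 or higher treatment-related non-hematological toxicity. A list of exceptions follows. It includes "Grade 3 transient ALT/AST elevations which are rapidly reversible and not leading to subsequent delays", and such participants "may continue treatment at the same prior dose without any dose reduction being applied", on condition that the toxicity receives optimal concomitant treatment.
- **Section A6-2.4.1.2 (Management of Liver Abnormalities).** For Grade 3/4 increases in liver function tests, "dose reduction and/or delays until resolution to at least Grade 1 are indicated". The section then names Table A6-4 as the guideline for lurbinectedin-related hepatotoxicity.
- **Table A6-4.** For Grade 3 or higher transaminase elevations: interrupt, then "Restart lurbinectedin at a reduced dose when AST and ALT" are at or below 2.5 × ULN, or 5 × ULN with documented metastatic liver disease.

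Table A6-2 sets the same ULN multiples as a condition for Day 1 lurbinectedin but gives no dose level. Section A6-2.1 also fixes the consequences of a reduction. "Up to 2 individual lurbinectedin dose reductions are allowed" (Table A6-1: 3.2, then 2.6, then 2.0 mg/m²). "Once the dose has been reduced for an individual participant, it must not be re-escalated again under any circumstances". At 2 mg/m², a participant who "experiences a toxicity that would warrant a lurbinectedin dose reduction, treatment with lurbinectedin must be permanently discontinued".

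**The concern.** A site that starts from A6-2.1 and a site that starts from the liver section can treat the same laboratory result differently. One keeps the dose; the other reduces it permanently. Neither would be deviating from the text it followed.

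The protocol itself gives dose weight. Section 4.3.5 treats dose intensity as important for lurbinectedin's effect, and Section 4.3.1 reports lower efficacy at lower doses. SAP 4.5.1 summarizes maintenance exposure and dose intensity, and SAP 4.3.5 summarizes adverse events leading to treatment modification or discontinuation. Those Arm A summaries would partly reflect which passage a site used, rather than tolerability alone.

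**Working it through.** The plan states no figure to reproduce. The check is a comparison of the texts, followed by arithmetic for scale only.

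**Step 1. Dose instruction.**

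| Event | A6-2.1 | A6-2.4.1.2 | Table A6-4 |
|---|---|---|---|
| Grade 3 ALT/AST: transient, rapidly reversible, optimally treated, no delay | Same prior dose allowed | Reduction, delay, or both | Interrupt, restart reduced |
| Other Grade 3/4 ALT/AST, treatment-related | Reduced dose after recovery | Reduction, delay, or both | Interrupt, restart reduced |

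In the first row, A6-2.1 and Table A6-4 conflict directly. In the second row those two agree, but the prose that introduces the table would be satisfied by delay alone.

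**Step 2. Recovery condition.** A6-2.4.1.2 asks for at least Grade 1, with no allowance for liver metastases. Tables A6-4 and A6-2 ask for ≤ 2.5 × ULN, or ≤ 5 × ULN with metastatic liver disease. The wording differs, but the documents do not reproduce the CTCAE cut-offs, so the size of the difference cannot be judged from them.

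**Step 3. Consequence of the choice, for an event that meets the A6-2.1 exception.**

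| Current dose (mg/m²) | Under A6-2.1 | Under Table A6-4 | Change from 3.2 under Table A6-4 |
|---|---|---|---|
| 3.2 | 3.2 | 2.6 | (3.2 − 2.6)/3.2 = 18.75% lower |
| 2.6 | 2.6 | 2.0 | (3.2 − 2.0)/3.2 = 37.5% lower |
| 2.0 | 2.0 | No lower level: permanent discontinuation | Treatment ends |

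**Step 4. Scale.** Inputs:

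- Protocol A6-1.1.2, single-agent lurbinectedin at 3.2 mg/m², regardless of relationship: Grade 3/4 ALT 6.4% (Grade 4 0.4%) and Grade 3/4 AST 3.2% (Grade 4 0.5%).
- SAP 2.2.3: target of 450 randomized, 1:1, so 450/2 = 225 in Arm A.

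The exception covers Grade 3 only, so Grade 4 is removed:

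- ALT: 6.4% − 0.4% = 6.0%; 0.060 × 225 = 13.5.
- AST: 3.2% − 0.5% = 2.7%; 0.027 × 225 = 6.1.
- Any Grade 3 transaminase elevation: about 14 if every AST case is also an ALT case, and 13.5 + 6.1 = 19.6, about 20, if there is no overlap.

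The share that is transient, rapidly reversible and without delay is not given. The number meeting the exception is therefore anywhere from 0 to that total.

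**The case against.** The best defence is that the texts can be read together. A6-2.1 is the dose-modification section, it states a general rule, and it then names ALT/AST among the exceptions. Table A6-4 would restate the general rule, the exception would qualify it, and the and/or wording would accommodate both outcomes. This is plausible, but the protocol does not say it. The exceptions follow the A6-2.1 list, the liver section sends the reader to Table A6-4, and the table neither mentions the exception nor refers back. The reading also leaves the second row of Step 1 unresolved: delay alone in the prose, reduction at restart in the table.

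A second argument narrows the point, and it stands. The exception excludes events that lead to a delay. Scheduled on-treatment chemistry in Table 2 falls on Day 1, and Table A6-2 already withholds lurbinectedin above its ULN limits. If Grade 3 lies above those limits, a Grade 3 value found on Day 1 causes a delay and falls outside the exception. The direct clash then mainly concerns values that recover before the next Day 1. A reader might infer that every transient Grade 3 elevation is caught; the conditions in A6-2.1 do not support that.

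A reader might also take the raw Grade 3/4 rates as the number affected (0.064 × 225 = 14.4 for ALT; 0.032 × 225 = 7.2 for AST). The documents do not support that either. These are single-agent rates, count events regardless of cause, include Grade 4, and say nothing about overlap or transience.

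Nor do the documents support reading this as an absence of liver safeguards. Re-evaluation before re-treatment is mandatory under A6-2.4.1.2, the Table A6-2 limits apply before dosing, and the stopping criteria in Section 7.1.1 remain in force.

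**Conclusion.** The inconsistency is real and limited. It has three parts: a direct conflict between A6-2.1 and Table A6-4 for transient, rapidly reversible, optimally treated, no-delay Grade 3 elevations; a looser conflict between A6-2.4.1.2 and Table A6-4 over whether reduction is required at all; and a recovery condition worded in two ways. It goes beyond missing detail because a reduction cannot be reversed and, at the lowest level, becomes discontinuation.

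The ceiling is about 14 to 20 Arm A participants with any Grade 3 transaminase elevation. It assumes that single-agent rates carry over to the combination and that Arm A has about 225 participants. It bounds the first conflict only; it does not estimate how many participants were affected.

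One might infer that the PFS and OS comparisons are compromised. The documents do not support this: both are analyzed as randomized, and early discontinuation is handled by treatment policy. The effect falls on Arm A exposure and its interpretation. The Version 8 rationale reports that the final OS cut-off has been reached, so new wording cannot alter exposure already in those data. Correction is still worthwhile, at moderate priority.

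**What to change.** Reconcile A6-2.1, A6-2.4.1.2 and Table A6-4, together with Table A6-2, so that the dose instruction, any exception with all its conditions, and the recovery threshold agree and cross-refer. Which dose rule and which threshold apply is the sponsor's clinical decision; this review takes no position on it.

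The cost is protocol wording in an amendment. Its main benefit is to participants still receiving lurbinectedin. For data already collected, the report should note the inconsistency beside the Arm A dose-reduction and exposure summaries, so that liver-related reductions are not read as a pure measure of tolerability.

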### **A6-2.4.1.3 Management of Gastrointestinal Adverse Events**

Premedication with IV serotonin (5-HT3) antagonists (ondansetron or equivalent) plus a steroid (dexamethasone or equivalent) will be provided before the first lurbinectedin administration (Cycle 1, Day 1; see Section 6.1.3 for more details on prophylactic medications). The requirement for premedication for anti-emetic prophylaxis for the subsequent cycles (i.e., Day 1, Cycle 2 and subsequent cycles) should be evaluated on an individual basis, and its administration left to investigator judgment. In addition, extended 5-HT3 antagonists and/or steroids can be administered orally for 3–5 days after drug infusion, if necessary. Prokinetics and additional anti-emetic treatment should be evaluated on an individual basis; however, aprepitant or any other neurokinin-1 (NK-1) antagonist or related Substance P-antagonists (except rolapitant) must NOT be administered with lurbinectedin due to the risk of lurbinectedin overexposure and the resulting severe and prolonged myelosuppression.

### **A6-2.4.1.4 Management of Renal Abnormalities**

Lurbinectedin may cause dehydration due to nausea/vomiting, as well as other toxicities such as diarrhea, or even sepsis, which may lead to secondary renal impairment (pre-renal causes). Hence, a normal blood pressure and adequate participant hydration are required before treatment with lurbinectedin.

Regular monitoring of plasma creatinine levels before each new cycle, as well as electrolytes will be performed.

## **Appendix 6: Safety Plan: Management of Identified and Potential Risks**

---

A renal function with creatinine clearance of at least 30 mL/min is required at baseline, as well as re-treatment criterion. Assessment of creatinine clearance before the administration of each new cycle will be performed.

### **A6–2.4.1.6 Management of Infusion Site Reactions**

Careful handling of lorbrena is advised. Although short infusion times (one hour) make extravasation unlikely, episodes of extravasation were reported in three participants (0.5%) treated with single-agent lorbrena at 3.2 mg/m^2 in Phase II and III studies.

Extravasation of lorbrena may result in skin and soft tissue injury, including necrosis requiring debridement. Use of a central venous catheter is suggested to reduce the risk of extravasation, particularly in participants with limited venous access. Participants must be monitored for signs and symptoms of extravasation during lorbrena infusions. In the event of extravasation, the infusion must be discontinued immediately, the infusion catheter must be removed, and the participant must be monitored for signs and symptoms of tissue necrosis. The time to onset of necrosis after extravasation may vary.

